**A Prospective Randomized Clinical Trial Evaluating Surgical Conditions during
Laparoscopic Bariatric Surgery with Deep *versus* Moderate Neuromuscular
Blockade**

PI: [name], MS¹
Professor

Co-PI: [name], MD¹
Resident

Co-I [name]
Associate Professor

[name]
Associate Professor

Co-I: [name], MD²
Associate Professor
Director, Missouri Bariatric Services

Statistician: [name].
Research Assistant Professor³

¹Department of Anesthesiology and Perioperative Medicine

²Department of General Surgery, Division of Bariatric Surgery

³Department of Health Management and Informatics, Office of Medical Research
University of Missouri
Columbia, Missouri 65212

Version 1: January 5, 2016
IRB project number: 2004620

Contact Information: [name], MS
Department of Anesthesiology and Perioperative Medicine
University of Missouri-Columbia

[name]

[name]

[contact]

[contact]

Email: [contact]

2.1 Objectives:

This prospective, randomized, single-blind trial will randomize patients undergoing laparoscopic bariatric surgery to either deep (0 twitches, 1-2 PTC) or moderate (reappearance of T2) neuromuscular blockade (NMB). Within each NMB group, patients the initial insufflation pressure will be either 10 or 15 mm Hg:

Primary Endpoint:

1. Surgeon initial satisfaction with operating conditions

Secondary Endpoints:

1. Percentage of procedures that can be performed at low (10 mm Hg) versus high (15 mm Hg) insufflation pressures at each level of NMB
2. Percentage of procedures requiring additional NMB and/or insufflation pressures to achieve satisfactory intraoperative surgical conditions
3. Quantification of postoperative pain medication requirements with deep versus moderate NMB

2.1.1 Clinical Hypotheses:

Primary Hypothesis:

We hypothesize that deep neuromuscular block (NMB)

1. provides better intra-operative surgical conditions than moderate NMB during laparoscopic bariatric surgery

Exploratory Hypotheses:

We hypothesize that deep neuromuscular block (NMB):

1. allows the use of lower insufflation pressures during laparoscopic bariatric surgery
2. decreases postoperative pain and the need for postoperative pain medication

2.2 Background & Rationale:

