Recently, there has also been interest in maintaining low insufflation pressure during laparoscopic surgery because lower pressures may decrease postoperative pain.¹⁰ It is hypothesized that deep NMB will provide good surgical conditions and minimize postoperative pain at low insufflation pressures of 7 to 10 mmHg, but this theory has not been adequately evaluated, especially in obese patients.

At the present time, there is no conclusive evidence that surgeons need deep NMB for laparoscopic bariatric surgery and even that surgeons can discriminate between moderate and deep NMB.¹¹ The goal of this prospective, randomized, assessor-blinded controlled trial is to test the hypothesis that deep NMB provides optimal surgical conditions during laparoscopic bariatric surgery in the morbidly obese patient. In addition, we will determine if deep NMB allows the surgeon to utilize lower insufflation pressure and decreases postoperative pain requirements after laparoscopic bariatric surgery.

2.3 Study Design:

Study design: prospective, randomized, assessor-blinded controlled trial that will be performed at a single academic hospital. The surgeons, subjects, and individuals performing the postoperative assessments will be blinded to the study group assignment. The anesthesia providers responsible for the clinical care of the patients will be aware of the rocuronium NMB treatment group and NMB and insufflation status throughout the surgical procedure.

2.4 Study Design:

2.5 Study Procedures:

- I. Patient population: this study will enroll 145 adults undergoing elective laparoscopic bariatric surgery. Our aim is to randomize 140 patients and this will allow 5 subjects to drop out of the study after enrollment.
- II. Inclusion criteria:
 - a. Age \geq 18 years
 - b. ASA I-III
 - c. BMI \geq 35
- III. Exclusion criteria:
 - a. Inability to obtain written informed consent
 - b. Pregnancy or breastfeeding
 - c. Allergy to rocuronium, sugammadex, or any anesthetic agents used in the protocol
 - d. Known or suspected neuromuscular disorders
 - e. Significant renal disease with a serum creatinine \geq 2 mg/dl
 - f. Significant liver disease
 - g. A family history of malignant hyperthermia

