- b. Fentanyl PCA will be started in the postanesthesia recovery room and continued for the first 24 – 48 hours after surgery.

VIII. Perioperative assessments

- a. Surgeon satisfaction – the primary endpoint is the surgeon's satisfaction with the level of NMB during surgery at the start of the case (the initial score). The satisfaction level will be rated with a five-point ordinal scale ranging from 1 (extremely poor) to 5 (optimal conditions). This scale is outlined in detail in table 1 (page 15) and is adopted from a previously published studies.⁶ For each patient, the first surgeon satisfaction rating during the procedure (prior to any rescue measure) will be the primary outcome measure.
- b. During the laparoscopic procedure, the surgeon will score the surgical working conditions. The first rating will occur when the NMB level is stable at either deep or moderate block (per randomization) and the intra-abdominal pressure is either 10 or 15 mm Hg per a second randomization list. The surgeon will be blinded to the insufflation pressure at this point. If the conditions are rated as extremely poor or poor (surgical rating of 1-2, Table 1), the following steps will be taken in an incremental manner. The surgeon may also request rescue

treatment if the surgical rating scale is 3 (acceptable), but he anticipates deterioration in the surgical condition during the procedure :

1. Increase the insufflation pressure to a maximum of 15 mm Hg –the surgeon will reassess the surgical field after the intra-abdominal pressure is stable at 15 mm Hg for 2-3 minutes. At this point the insufflation pressure will remain at 15 mm Hg for the remainder of the procedure.
2. Additional muscle relaxation – if the surgeon rates the working conditions as 1 (extremely poor) or 2 (poor) after increasing the insufflation pressure to 15 mm Hg, the surgeon may then request additional muscle relaxant. At this point the anesthesia provider will check the level of NMB. If the patient is in the moderate group and has 1 or more twitches, the anesthesia provider will administer a bolus dose of rocuronium, 0.3 mg/kg iv. If the patient has only 0-1 PTC, the anesthesia provider will administer an equal volume of iv saline. The surgeon will rate the surgical working conditions at 2-3 minutes after the additional dose of medication.

- c. Intra-abdominal insufflation pressures and TOF ratio measurements will be recorded every 15 minutes during the procedure.

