- d. Surgeons will be asked to rate their satisfaction with the surgical field every 30 minutes during the procedure.
- e. Perioperative variables will also be recorded including the duration of surgery, time from administration of NMJ reversal (sugammadex) to extubation, time from end of surgery to exit from the OR, time in the PACU, and length of hospital stay.
- f. Postoperative verbal pain levels (0 = no pain to 10 = worst imaginable pain) and opioid requirements will be assessed daily. Patients will also be asked about the presence or absence of shoulder pain.

- g. Postoperative variables including the need for postoperative mechanical ventilation, re-intubation, residual paralysis, pneumonia, infections, and other adverse events during the hospital stay. The need for ICU admission and length of hospital stay will also be collected.

2.6 Study Duration:

The Missouri Bariatric Service at the University of Missouri-Columbia performs over 600 bariatric procedures per year. The Director for this service, [name] [name], is a co-investigator on the study. He has 3 full day operating blocks per week and we estimate that we can easily enroll 15 patients per month.

We estimate that patient enrollment can be completed in 9 months. We will need an additional 3 months after enrollment is complete for data analysis and abstract/manuscript preparation.

Statistical Analysis and Sample Size Justification:

[figure not shown]
Data analysis will be based on an intent-to-treat approach. The primary endpoint will be the first surgeon satisfaction rating measured on a five-point ordinal scale (Table 1). The experimental layout is a randomized two-factor design so the primary analysis will be the two-way Analysis of Variance (ANOVA) with interaction. A statistically significant interaction will be followed by pairwise comparisons to identify and estimate treatment combination differences. The standard ANOVA assumes a normally distributed outcomes with homogeneous variances and so the robustness of the results will be checked against an aligned-rank test for the two-way layout.¹²

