Secondary outcomes will be time to extubation or discharge, and total pain medication requirements. The same two-way analysis as described for surgeon satisfaction will be used for each of these endpoints. Residuals will be examined and need for a modest transformation or rank-based methods considered. Moderate and deep NMB will also be compared with respect to the proportion of cases randomized to low insufflation pressure that were completed at low pressure. The chi-square test of proportions will be used for that analysis.

Sample size – Sample size estimates are based surgeon satisfaction rating as this is the primary outcome. Figure 3 of Martini et al.⁶ gives the frequency distribution of the surgeon satisfaction score under moderate and deep block. Scores for the moderate block have the greatest variability and so for sample size purpose the proportions from Fig. 3 were used to estimate the standard deviation of the surgeon satisfaction score ($\sigma = 1.1$). Based on literature and clinical judgement we powered the study to have at least 80% power to detect statistically significant ($p < 0.05$) effects for the main effects and interaction term in a two-way analysis of variance assuming the following configuration of mean satisfaction scores and a common standard deviation of 1.1.

		Pressure	
		10mmHG	15mmHG
Block	Moderate	2.5	4.0
	Deep	4.3	4.8

Power curves for each of the ANOVA effects are displayed in Figure 1. The required minimum sample size is 108 subjects, allocated 27 per treatment combination. To guard against potential optimism in these calculations (actual variances could be larger or effects smaller) we intend to recruit 35 subject per treatment combination for a total sample size of 140.

Power calculations were carried out using GLMPOWER procedure in SAS v 9.3.

Specific Drug Supply Requirements:

The anesthetic agents utilized in this study (including rocuronium) are routinely used for this type of surgery and are acceptable patient costs. However, sugammadex just received FDA approval in December 2015 and is not currently used for NMB reversal at our institution. We will receive adequate supplies of sugammadex from Merck &Co. so that there will be no charge to the patients for this medication.

2.11 References:

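### The planned block effect on postoperative pain medication includes the effect of unequal rescue to 15 mm Hg, so by itself it cannot show that block depth reduces opioid need at a given pressure

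*Combined protocol and SAP*

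**What the plan says.** Section 2.1 lists as a secondary endpoint: "Quantification of postoperative pain medication requirements with deep versus moderate NMB". Section 2.1.1 gives two separate exploratory hypotheses about deep block. Hypothesis 1 is that it "allows the use of lower insufflation pressures during laparoscopic bariatric surgery". Hypothesis 2 is that it "decreases postoperative pain and the need for postoperative pain medication".

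In the Statistical Analysis section, "Data analysis will be based on an intent-to-treat approach", and for the surgeon's first rating "the primary analysis will be the two-way Analysis of Variance (ANOVA) with interaction". Pairwise comparisons follow only if the interaction is significant. For time to extubation or discharge and for total pain medication, "The same two-way analysis as described for surgeon satisfaction will be used for each of these endpoints". The same section plans a chi-square test, moderate against deep, of the proportion of low-pressure cases completed at low pressure.

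Section 2.5, item VIII, takes the primary rating before any rescue. A rating of 1-2 then triggers stepwise rescue, and a rating of 3 may do so. The first step raises pressure to at most 15 mm Hg: "At this point the insufflation pressure will remain at 15 mm Hg for the remainder of the procedure". If the rating is still 1-2, the surgeon may request more relaxant, and a moderate-group patient who has twitches then receives a rocuronium bolus. Pressure is recorded every 15 minutes. Section 2.2 gives the reason for interest in low pressure: "lower pressures may decrease postoperative pain".

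**The concern.** The two-way analysis fits the primary rating well, because at that moment every patient is at the assigned block and the assigned pressure. Pain medication is measured after rescue has changed the pressure in some patients, and the plan's own assumptions imply that this happens far more often in moderate/10 than in deep/10. If hypothesis 1 is true, the two 10 mm Hg groups end up operated on at different pressures. If low pressure also reduces pain, as the background suggests, a deep-versus-moderate difference in opioid use follows even when depth does nothing else.

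What is at stake is interpretation. The plan lists the two hypotheses separately, but its opioid analysis does not separate them. The one randomized contrast without a pressure difference, deep/15 versus moderate/15, is reached only through a significant interaction. A positive block effect could then be reported as evidence for hypothesis 2 when it only restates hypothesis 1.

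**Working it through.** **Inputs from the plan (sample size paragraph).** Mean first rating: moderate/10 2.5, moderate/15 4.0, deep/10 4.3, deep/15 4.8. Common SD 1.1. Planned size 35 per cell, 140 in total. Rescue trigger (item VIII.b): rating 1-2, optionally 3.

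**The plan's own figure.** The stated minimum of 108 (27 per cell) for at least 80% power on every ANOVA effect does not reproduce. The interaction contrast is (4.8 - 4.3) - (4.0 - 2.5) = -1.0. Its power is 65% at 27 per cell and 76% at 35, and 80% needs 39 per cell. This point does not rest on the 108. It uses only the means and the SD.

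**Step 1: share moved to 15 mm Hg at the first rating.** Normal model, share = Φ((cut - mean)/1.1), with the cut midway between adjacent ratings.

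| Trigger | Moderate/10 | Deep/10 | Difference |
|---|---|---|---|
| Ratings 1-2 (cut 2.5) | Φ(0) = 50.0% | Φ(-1.64) = 5.1% | 44.9 points |
| Every 3 also rescued (cut 3.5) | Φ(0.91) = 81.8% | Φ(-0.73) = 23.4% | 58.5 points |

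The documents do not give the shape of the distribution. A maximum-entropy distribution on 1-5 with the same mean and SD gives 53% and 9.5% for ratings 1-2. Over all 1-5 distributions with those means and SD, the share rated 1-2 lies between 31% and 83% in moderate/10 and between 4% and 17% in deep/10. The ranges do not overlap, so the direction does not depend on the normal model.

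**Step 2: consequence for pain medication.** Let d be the opioid effect of 15 versus 10 mm Hg in SD units. It is an assumption, because the documents give no value. Set the direct effect of depth to zero, so that each cell mean is d times the share operated on at 15 mm Hg. Both 15 mm Hg cells then equal d.

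- Moderate minus deep at 10 mm Hg: (0.500 - 0.051)d = 0.45d, or (0.818 - 0.234)d = 0.58d.
- Block main effect, half of that: 0.22d, or 0.29d.
- Interaction contrast: 0.45d, or 0.58d.

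Taking the shape bounds for ratings 1-2 at their extremes widens the main effect to between (0.31 - 0.17)/2 = 0.07d and (0.83 - 0.04)/2 = about 0.39d.

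**Step 3: chance of a significant result at 35 per cell.** Noncentral F with 1 and 136 df. The standard error of the main effect is 2/√140 = 0.169 SD, and of the interaction contrast √(4/35) = 0.338 SD.

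| d (SD) | Block main effect | Interaction |
|---|---|---|
| 0.3 | 7-8% | 7-8% |
| 0.5 | 10-14% | 10-14% |
| 0.8 | 18-28% | 18-28% |

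The two columns agree because the interaction contrast and its standard error are each twice those of the main effect. The test that would open the pairwise comparisons is therefore no more likely to be significant than the block effect it would help to explain.

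**Step 4: the 15 mm Hg contrast.** Pressure cannot be raised above 15, so deep/15 and moderate/15 do not differ in pressure. Relaxant boluses remain possible: Φ((2.5 - 4.0)/1.1) = 8.6% of moderate/15 start at ratings 1-2. The standard error is √(2/35) = 0.239 SD, and 0.239/0.169 = 1.41.

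**The case against.** The strongest reply is that pressure is a mediator here and not a source of bias. If deep block spares a patient the rise to 15 mm Hg and opioid need falls as a result, that is a real effect of assigning deep block. The plan specifies intent to treat, section 2.1 defines the second factor as the initial pressure, and section 2.2 presents good conditions and less pain at low pressure as one idea. Nothing says that hypothesis 2 means an effect of depth at fixed pressure. All of this stands. A reader might infer from the table in step 3 that the analysis has an inflated false-positive rate. It does not: the total effect in that model is not zero, so those figures are power for a true strategy effect.

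Three further replies also stand. The plan already compares low-pressure completion between block groups, so unequal rescue would be visible. No endpoint or hypothesis asks for the effect of pressure on opioids, so a reader who objects that rescue weakens the pressure comparison is raising a question the plan does not pose. And deep/15 versus moderate/15 is not a pure depth contrast because of the boluses, and it leaves out the low-pressure setting that section 2.2 has in mind. It therefore should not replace the planned analysis or serve as the only estimate of depth.

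None of this supplies what is missing: a statement of which effect the opioid comparison estimates, and a randomized contrast free of the pressure difference that is reported regardless of the interaction test.

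**Conclusion.** The planned analysis is valid, and the point concerns what it can support. The block effect on pain medication is the total effect of the assigned strategy including rescue. It cannot show that depth reduces opioid need at a given pressure, because it can arise entirely through hypothesis 1. A reader might go further and conclude that the ANOVA is wrong for this endpoint. The intent-to-treat specification does not support that.

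With no direct depth effect, the block main effect is 0.22d to 0.29d under the normal model, with 10-14% power at d = 0.5 SD. This rests on the plan's means and SD, on an assumed d, and on the premise that higher pressure raises opioid need. How often rescue occurs depends on the shape of the rating distribution, but moderate/10 exceeds deep/10 for ratings 1-2 under every shape consistent with the inputs. The hypothesis is exploratory, so this is an inexpensive clarification worth making before analysis.

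**What to change.** In the secondary-outcome paragraph of the Statistical Analysis section:

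1. Keep the two-way ANOVA as the planned analysis of total pain medication, and state that its block effect is that of the assigned strategy, including rescue to 15 mm Hg.
2. Whether or not the interaction is significant, report deep/15 versus moderate/15 with a 95% CI as a supportive estimate of the block effect without a pressure difference. Note that relaxant boluses in moderate/15 (about 9% start at ratings 1-2) pull it toward no effect.
3. Present the already planned low-pressure completion proportions next to the opioid result.
4. State that a block effect seen only at 10 mm Hg will not be read as support for hypothesis 2 independent of hypothesis 1.

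This compares groups as randomized and does not adjust for the pressure actually used. The cost is a few sentences, with no new data or patients. The supportive contrast uses 70 of 140 patients, so its standard error is 1.41 times that of the main effect (0.239 versus 0.169 SD). Its 95% CI will be about ±0.47 SD wide (1.96 × 0.239), and a null result there should not be read as proof of no depth effect.

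### The planned 80% power for the interaction is not met: the plan's own means and SD give 65% at 27 per cell and 76% at the planned 35 per cell

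*Combined protocol and SAP*

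**What the plan says.** The section headed Statistical Analysis and Sample Size Justification states that "the primary analysis will be the two-way Analysis of Variance (ANOVA) with interaction". A significant interaction leads to pairwise comparisons of the treatment combinations.

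In the sample size paragraph of that section, the authors write that "we powered the study to have at least 80% power" to "detect statistically significant ($p < 0.05$) effects for the main effects and interaction term", "assuming the following configuration of mean satisfaction scores and a common standard deviation of 1.1". The table that follows gives means of 2.5 (10 mmHg) and 4.0 (15 mmHg) under moderate block, and 4.3 and 4.8 under deep block. The conclusion is: "The required minimum sample size is 108 subjects, allocated 27 per treatment combination".

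As protection against variances larger, or effects smaller, than assumed, the plan adds that "we intend to recruit 35 subject per treatment combination for a total sample size of 140". The calculations are attributed to SAS GLMPOWER. The power curves (Figure 1) are not reproduced in the text available for review.

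**The concern.** The power claim names three effects, and the least well powered of them sets the sample size. In a 2×2 layout the interaction is a difference of differences, so its standard error is twice that of a main-effect difference. Here the pressure main effect and the interaction contrast are both 1.0 point, so the interaction needs roughly four times as many subjects. A minimum of 27 per cell looked too small for it.

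Two things are at stake. The interaction is part of the primary analysis and decides whether pairwise comparisons follow. It also bears on the stated aim of learning whether deep block permits lower insufflation pressure. The plan does not say how a non-significant interaction will be interpreted. A reader who believes the test had 80% power or more could take such a result as better evidence of no dependence on pressure than it is.

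**Working it through.** **Inputs**, all from the sample size paragraph: cell means 2.5 / 4.0 (moderate, 10 / 15 mmHg) and 4.3 / 4.8 (deep, 10 / 15 mmHg); common SD σ = 1.1; α = 0.05; target power 80%; n = 27 or 35 per cell. The ANOVA F test on 1 df is equivalent to a two-sided t test.

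**Effects**

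- Block: (4.3 + 4.8)/2 − (2.5 + 4.0)/2 = 4.55 − 3.25 = 1.3
- Pressure: (4.0 + 4.8)/2 − (2.5 + 4.3)/2 = 4.4 − 3.4 = 1.0
- Interaction: (4.0 − 2.5) − (4.8 − 4.3) = 1.5 − 0.5 = 1.0

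**Power.** For a balanced 2×2 ANOVA, power comes from the noncentral F distribution with 1 and 4n − 4 df. The noncentrality is:

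- main effect of size d: λ = n·d²/σ², because SE = σ/√n
- interaction contrast of size d: λ = n·d²/(4σ²), because SE = 2σ/√n

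For the interaction:

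- n = 27: λ = 27 × 1.0² / (4 × 1.21) = 5.58, 104 error df, power 64.8%
- n = 35: λ = 35 / 4.84 = 7.23, 136 error df, power 76.1%

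**Attempt to reproduce the plan's minimum**

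| Effect | Power, 27 per cell | Power, 35 per cell | Smallest n per cell for 80% |
|---|---|---|---|
| Block (1.3) | >99.9% | >99.9% | 7 |
| Pressure (1.0) | 99.7% | >99.9% | 11 |
| Interaction (1.0) | 64.8% | 76.1% | 39 |

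The interaction reaches 79.5% at 38 per cell (152) and 80.5% at 39 per cell (156). The stated 27 per cell is not reproduced: it is far above what the main effects need and below what the interaction needs.

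**Cross-checks of the interaction power.** A normal approximation gives 65.6% at 27 per cell and 76.7% at 35. A simulation of 100,000 runs gives 64.7% and 76.0%.

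**Other readings tried**

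- A one-sided 5% test gives 75.9% at 27 per cell and 84.9% at 35, with a minimum of 31 per cell (124). That is still not 27, and the plan specifies no one-sided test.
- 90% power for the interaction needs 52 per cell.
- The overall 3-df test has over 99.9% power at 27 per cell.
- Pairwise cell comparisons and permutations of the four means among the cells do not lead to 27 either.

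**What would give 27.** An interaction contrast of 1.2 gives λ = 27 × 1.44 / 4.84 = 8.03 and power 80.2%; at 26 per cell it gives 78.7%. So 27 is exactly the minimum for a contrast of 1.2. Moving any one of the four means by 0.2 in the right direction produces that contrast (for example deep/15 mmHg at 4.6). An SD of about 0.92 with the printed means would also do it. The documents do not say which, if any, applies.

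**The margin.** At 35 per cell, power for the interaction falls to 69% if the SD is 1.2 (λ = 35 / 5.76 = 6.08), and to 67% if the contrast is 0.9 (λ = 35 × 0.81 / 4.84 = 5.86). These are the kinds of departure the extra subjects were meant to absorb.

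**The case against.** The strongest counter-argument concerns the SD. Scores run from 1 to 5, so a cell with mean 4.8 cannot have an SD above √((5 − 4.8)(4.8 − 1)) = √0.76 = 0.87. The plan also says that 1.1 came from the more variable moderate-block scores. Keep 1.1 in three cells and put 0.87 in the deep/15 mmHg cell: the average variance is (3 × 1.21 + 0.76)/4 = 1.0975, and interaction power is about 80.1% at 35 per cell and 69.0% at 27. If both deep cells had an SD of 0.87, which is an assumption, the figures would be about 84% and 74%. This stands as a reason to regard 39 per cell as the requirement under a conservative common SD. It does not rescue the plan's statement, which rests on a common SD of 1.1, and 108 stays short of 80% in each case.

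Other points are fair but limited:

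- The primary hypothesis concerns deep against moderate block, and that main effect is amply powered. At the planned 140 the interaction shortfall is about 4 percentage points; the larger gap belongs to 108, which the trial does not intend to use. This limits the consequence, not the error.
- A misprinted mean or SD may be the whole explanation, and no single cell can be singled out. Figure 1 might settle it. Either way, the printed inputs and the printed sample size contradict each other.
- The plan nowhere says it will treat a non-significant interaction as evidence of no interaction, so over-reading is a risk and not a stated intention.

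**Conclusion.** The concern holds. With the plan's means, common SD of 1.1 and two-sided 5% F tests, power for the interaction is 64.8% at 108 subjects and 76.1% at 140. The type II error is 35% and 24% respectively, against the 20% implied. The requirement is 156, so 140 is 16 subjects below it and not, as the plan has it, 32 above the minimum. The shortfall at 140 depends on the common SD of 1.1; the failure of 108 also survives the lower deep-block SDs considered above. Both main effects keep over 99% power at either size, so the design is sound for the primary hypothesis. The stated power for the interaction is not, and it must be corrected.

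**What to change.** Replace the power statement with wording such as: 140 subjects (35 per cell) give over 99% power for each main effect and 76% for the tabulated interaction of 1.0 point, at a common SD of 1.1 and two-sided 5%; the interaction contrast detectable with 80% power is 1.05 points; 80% power for a 1.0-point contrast would need 39 per cell. (Check: 35 × 1.05² / 4.84 = 7.97, power 80.1%.)

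Delete the minimum of 108, and delete the claim that 140 provides a margin for the interaction.

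Before doing so, check the GLMPOWER input. If a different cell mean or SD was used, correct the table or the SD and restate the power at 140 from the corrected values. If the sponsor prefers to rely on smaller SDs in the deep-block cells, those SDs should be stated and justified.

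The cost is protocol wording only. No patients are added and the analysis does not change; the reported interaction power becomes less favourable.
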